CLINICAL STUDY PROTOCOL

C. Kenneth and Dianne Wright
Center for Clinical and Translational Research

SAFEty Study of Early Infusion of Vitamin C for Treatment of Novel Coronavirus Acute Lung Injury

(SAFE EVICT CORONA-ALI)

Protocol Version: 1.83

Protocol Version IRB approved: 08/10/2021

VCU IRB Number: HM20018977

ClinicalTrials.gov Identifier: NCT04344184

IND: 149518

Study Personnel

Principal Investigator(s) [name]
Virginia Commonwealth University
Department of Internal Medicine
Pulmonary and Critical Care Medicine

[name], MD
Virginia Commonwealth University
Department of Internal Medicine
Pulmonary and Critical Care Medicine

Co-Investigators
[name]
Central Virginia VA Health System
Department of Internal Medicine
Gastroenterology and Hepatology Division

[name]
Department of Biostatistics
Virginia Commonwealth University,
Massey Cancer Institute

[name]
Virginia Commonwealth University
Department of Surgery
Division of Trauma Surgery

[name]
Virginia Commonwealth University
Department of Surgery
Division of Trauma Surgery

Clinical Coordinators: [name] and [name]
Virginia Commonwealth University
Department of Internal Medicine
Pulmonary and Critical Care Medicine

Regulatory Contact: [name]
Virginia Commonwealth University
Department of Internal Medicine
Pulmonary and Critical Care Medicine

Synopsis

Study Description

The purpose of this proof-of-concept, phase 2 safety study is to examine the safety profile, and possible therapeutic effects of high-dose, intravenous vitamin C (HDIVC) compared to placebo in hospitalized adult patients with novel Coronavirus COVID-19 and hypoxemia.

Objectives

To assess the safety profile of a 4-day (96-hour) intravenous vitamin C treatment protocol (comprised of four intravenous infusions a day, that is 50 mg/kg every 6 hours) in patients with laboratory-confirmed SARS-CoV-2 infection manifesting COVID-19 (Novel Coronavirus Disease 2019) with hypoxemia. While performing this phase 2 proof-of-concept, safety study, we will explore the following hypotheses:

Endpoint

Primary Endpoint (Safety): HDIVC infusion does not worsen the patients' outcomes, as measured by differences in the mean 9-point (from 0 to 8) World Health Organization (WHO) ordinal scale for disease improvement, between the two populations at 28, 60 and 90 days:

Table 1.

Patient State	Descriptor	Score
Uninfected	No clinical or virologic evidence of infection	0
Ambulatory	No limitation of activities	1
	Limitation of Activities	2
Hospitalized mild disease	Hospitalized, no oxygen therapy	3
	Oxygen by mask or nasal prongs	4
Hospitalized Severe Disease	Non-invasive ventilation or high-flow oxygen	5
	Intubation and mechanical ventilation	6
	Ventilation + additional organ support – vasopressors, renal replacement therapy, ECMO	7
Dead	Death	8

Secondary Endpoint A (Safety): Daily renal safety biomarkers on the day of randomization (Day 0), then day 1-7. These include (1) daily serum oxalate levels, (2) daily urine microscopic analysis for the presence of oxalate stones (3) daily random urine oxalate and 24-hour urine oxalate levels on days 5,7 and 14.

Secondary Endpoint B (Safety): acute kidney injury-free days at day 28, 90 (stemming from daily AKI assessment while patient is in the hospital).

Secondary Endpoint C (Safety): All-cause mortality to day 28, 60 90 (daily assessment).

Secondary Endpoint D: (Exploratory): COVID-19 and sepsis-specific inflammatory marker levels on Day 0, then on day 7. These include (1) ferritin, (2) D-dimer, (3) lactate dehydrogenase (LDH), (4) interleukin-6, and (5) Trough ascorbate plasma concentrations at 24 hours, 48 hours, 96 hours and final plasma concentration assessment at 168 hours.

Secondary Endpoint E: (Safety): Proportion of patients alive and free of respiratory failure through 28-days. (Respiratory failure defined as resource utilization requiring at least 1 of the following: Endotracheal intubation and mechanical ventilation, Oxygen delivered by high-flow nasal cannula (heated, humidified, oxygen delivered via reinforced nasal cannula

at flow rates >20L/min with fraction of delivered oxygen ≥ 0.5), noninvasive positive pressure ventilation, extracorporeal membrane oxygenation).

Secondary Endpoint F: (Safety): Proportion of patients alive and free of invasive mechanical ventilation at 28-days.

CLINICAL STUDY PROTOCOL

C. Kenneth and Dianne Wright
Center for Clinical and Translational Research

Study Population

Adult hospitalized patients who have central laboratory-confirmed COVID-19 (Novel Coronavirus Disease-2019, based on a positive SARS-CoV-2 RT-PCR confirmed within 72 hours before enrollment) and new-onset hypoxemia, defined as oxygen saturation (SpO₂) < 93% on pulse oximeter (WHO COVID-19 ordinal scale 3), or requiring any amount of supplemental oxygen (WHO COVID-19 ordinal scale 4-7) at (1) Virginia Commonwealth University Medical Center, and (2) Central Virginia Veterans Affairs (VA) Health System, Richmond, Virginia

Accrual Ceiling

The accrual ceiling for this safety trial is a total of 60 patients, between the two centers.

Phase

Phase 2, proof-of-concept safety trial.

Description of Sites/Facilities Enrolling Participants

The study will involve 2 enrollment sites: (1) Virginia Commonwealth University Medical Center, and the (2) Central Virginia Veterans Affairs (VA) Health System, Richmond, Virginia.

Description of Study Intervention

1. A two-center, prospective, randomized, **double-blind**, placebo-controlled proof-of-concept safety study.
2. A maximum of 60 patients (30 in the treatment, and 30 in the placebo arm) will be enrolled between the two centers.
3. Participants will be randomized to receive either intravenous vitamin C infusion (mixed in 5% dextrose in water) or placebo infusion (5% dextrose in water) in a 1:1 manner.
4. All study drug doses will be administered via an intravenous central or peripheral line infusion. Should no central or peripheral line be available at the scheduled time of infusion, a call should be placed to the pharmacy to determine if the study drug may be co-infused into the line that is infusing a different drug. If co-infusion of study drug is contraindicated, then a maximum of 8 hours may delay study drug infusion. If clinical drug administration schedule is such that study drug will not have an available administration time beyond this delay, a dedicated new intravenous line (peripheral) should be inserted if the patient is agreeable.
5. The study drug will be double-blinded with an identical appearing placebo.
6. Active treatment duration will continue for 96 hours, or until study withdrawal.

[figure not shown]
Study Duration

[figure not shown]
The study will be completed in two phases: Phase 1 will end on day 28, and phase 2 at 90 day follow up.

Participant Duration

The participant duration will be 90 days. Participants will receive the 4-day treatment period (96-hour); if needed, the last study-specific blood work will be collected up to 7 days follow-up after enrollment. Data up to 28 days follow-up will be collected from medical records, standard of care procedures, and chart review. Follow up data and patient-reported outcome measures will be collected by phone visit at day 90.

Schema

Schedule of Activities (SoA)

Assessments	Day 0-1	Day 1-2	Day 2-3	Day 3-4	Day 5-7**	Day 8-14**	Day 15-21**	Day 22-28**	Day 60&90
WHO-COVID-19 SCALE	R	R	R	R	R	R*	R*	R*	
AKI, present and stage of AKI	R	R	R	R	R	R*	R*	R*	
Creatinine, serum (BMP also includes sodium, chloride, potassium, BUN, bicarbonate, glucose)	R	R	R	R	R	R*	R*	R*	
Fluid Balance and Urine Output	R	R	R	R	R	R*	R*	R*	
Microscopic urine analysis	R	R	R	R	R	R14 ^{AKI}	R21 ^{AKI}	R28 ^{AKI}	
Serum oxalate	R	R	R	R	R	R14 ^{AKI}	R21 ^{AKI}	R28 ^{AKI}	
Random urine oxalate	R	R	R	R	R				
24-hour urine oxalate collection					R5, R7	R14	R21 ^{AKI}	R28 ^{AKI}	
Alive and Free of ANY Respiratory Failure (yes/no)	R	R	R	R	R	R	R	R	
Alive and Free from INVASIVE mechanical ventilation (yes/no)	R	R	R	R	R	R	R	R	
Oxygen Device Oxygen Flow Air Flow [HFNC only] FiO2 [if not NC] Intubated last 24 hours? Date & time of last intubation Extubated last 24 hours or last week? Date & time of last Extubation ECMO	S	S	S	S	S	S	S	S	
Body Weight (kg)	S	S	S	S	S	S	S	S	

	Vital Signs, Mental Status, qSOFA	S	S	S	S	S	S	S	S	
	Maximum norepinephrine rate today	S	S	S	S	S	S	S	S	
	Maximum vasopressin rate today	S	S	S	S	S	S	S	S	
	Maximum dobutamine rate today	S	S	S	S	S	S	S	S	
	Had Cardiac Arrest today (or last week)?	S	S	S	S	S	S	S	S	
	Demographics Comorbidities Active Diagnoses Admission APR-DRG On O2 at home Y/N O2 liters at home Baseline creatinine Baseline CKD stage	S								
	Received Dialysis last 24 hours or last week	S	S	S	S	S	S	S	S	
	Received CRRT last 24 hours or last week	S	S	S	S	S	S	S	S	
	Any episode of hypoglycemia last 24hours and week [Glucose < 50]	S	S	S	S	S	S	S	S	
	Any clinical symptoms of kidney stones? Back pain, Flank pain Hematuria Visible stone passed Imaging consistent with new kidney stone	R	R	R	R	R	R	R	R	
	Today's CBC, Differential	R	R	R	R	R	R	R	R	

	including lymphocyte ratio, including potassium, magnesium and phosphorus, LDH, D-Dimer, CRP, Ferritin, ABG, Urinalysis all if performed for patient care, pregnancy test (if applies and was not obtained)									
	Bilirubin Total, AST, ALT, ALP, albumin	R				R7	S	S	S	
	Received Steroids last 24 hours or last week? Steroid type and daily cumulative dose [for daily assessment]	S	S	S	S	S	S	S	S	
	COVID-19 specific treatments, anticoagulants, and dosage: Remdesivir Dexamethasone Anticoagulants Other COVID-19 treatments	S	S	S	S	S	S	S	S	
	Any atrial arrhythmias over the last interval [afib, aflutter, SVT]	S	S	S	S	S	S	S	S	
	12-Lead EKG	R	S	S	S	S	S	S	S	S
	Any significant ventricular arrhythmias over the last interval [not PVCs]	S	S	S	S	S	S	S	S	
	Chest X-Ray Chest Computer Tomography	S	S	S	S	S	S	S	S	S
	24-hour urine oxalate on day 5 (after completion of the last dose)	S	S	S	S	R	S	S	S	S
	Lowest daily blood glucose Highest lactate dehydrogenase	RS	R	R	R	RS				

	(LDH), serum									
	Highest D-dimer, plasma									
	Highest ferritin, plasma									
	Highest C-reactive protein (CRP), plasma									
	IL-6, plasma									
	Baseline and Trough Ascorbic Acid (vitamin C levels)	R	R	R	R	R7				
	AKI free-days days	S	S	RS	S	S	S	S	S	
	Urinalysis evaluation for stones									
	Is the patient still hospitalized? If not Discharge date time								R	
	Total Ventilator-Free Days								R	
	Was the patient paralyzed for ARDS at any point?								R	
	Was placed on iNO at any point?								R	
	Was placed in a prone position at any point?								R	
	Was placed on ECMO at any point during this hospitalization? [VA or VV]								R	
	Did the patient had a tracheostomy at any point in this hospitalization?								R	R
	Date and Time of Death if applies								R	R
	Cause of Death if applies								R	R
	DNR? If yes when was DNR first placed								R	R
	Phone clinic follow-up patient-reported outcome measure									R

PROMIS Dyspnea Assistive Devices and Resources score (version 1.0).								
Footnotes								
The study protocol does not include phlebotomy (new stick) just for study labs for days 1-4. If labs are obtained for any other reason, then study labs marked as “R” will be collected as “add-on” to the hospital lab. The protocol does include study labs that will be used specifically for Research marked as RS.								
S = standard of care (when feasible), R = research (optional), RS: research specific including phlebotomy; BMP = basic metabolic profile, DNR = do not resuscitate, ECMO = Extracorporeal membrane oxygenation, iNO = inhaled nitric oxide, AKI = acute kidney injury, CRRT = Continuous renal replacement therapy (continuous dialysis), HD = Hemodialysis, CKD = Chronic kidney disease, CRP = C Reactive Protein, ABG = Arterial blood gas, CAM-ICU = ICU Delirium scale, IL-6 = Interleukin 6, afib = atrial fibrillation, aflutter = atrial flutter, SVT = Supraventricular Tachycardia, AST = Aspartate aminotransferase, ALT = Alanine aminotransferase, ALP = Alkaline phosphatase.								
R* IF the patient is in the hospital								
R7 only on day 7 within that interval								
R14 only on day 14 within that interval								
R21 only on day 21 within that interval								
R28 only on day 28 within that interval								
R14^{AKI} collect on day 14 if patient develops AKI and still in the hospital								
R21^{AKI} collect on day 21 if patient develops AKI and still in the hospital								
R28^{AKI} collect on day 28 if patient develops AKI and still in the hospital								
End of Study Definition								
Treatment protocol will continue for 4 days (96 hours), and, if needed, the last study-specific bloodwork will be collected on day 7. Study will end if patient is withdrawn from the study, or lost to follow-up. All subjects will be followed to day 28 for collection of clinical outcomes data through electronic health records (EHR) even though the treatment protocol will be completed by 96 hours from randomization at the latest. Secondary outcome data will be collected either during in-person (clinic) visit or via telephone at the 90-day follow-up. Only acceptable reasons for early study termination include consent withdrawal or loss to follow-up.								

Abbreviations

Abbreviation	Explanation
AE	Adverse Event
AKI	Acute Kidney Injury
ARDS	Acute Respiratory Distress Syndrome
Case Report Form	Case Report Form
CDC	Centers for Disease Control
CFR	Code of Federal Regulations
CLIA	Clinical Laboratory Improvement Amendments
CMP	Clinical Monitoring Plan
CONSORT	Consolidated Standards of Reporting Trials
COVID-19	Coronavirus Disease 2019
D5W	Dextrose 5% Water
DHHS	Department of Health and Human Services
DRE	Disease-Related Event
DSMB	Data Safety Monitoring Board
eCRF	Electronic Case Report Form
ED	Emergency Department
FIP	Feces-Induced Peritonitis
HDIVC	High-Dose Intravenous Vitamin C

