3.1 Objectives and Endpoints

OBJECTIVES	ENDPOINTS	JUSTIFICATION FOR ENDPOINTS
Primary		
WHO COVID-19 9-point Ordinal Scale Outcome	MEAN SCORE ON DAY 28, 60 AND 90	This ordinal scale captures a range of safety outcomes and is ideal for safety studies. If any other unanticipated clinical harms of high-dose intravenous vitamin C occur, will be captured on this outcome.
Secondary		
Renal safety biomarkers	Daily serum oxalate Daily urinalysis 24-hour urine oxalate on day 5	Measured biomarkers will provide a sensitive way to identify the mechanisms of oxalate nephropathy
AKI-free days at day 28 and 90	Renal-failure free days, with AKI defined by the KDIGO criteria (see table below).	This endpoint aims to identify long-term kidney outcomes among the two groups
All-cause mortality at 28 60 and 90 days	Safety Endpoint	If the therapy offers significant benefit, or harm, compared with placebo
Exploratory biomarkers	Ferritin, D-dimer, LDH, CRP, plasma IL-6 on day 7	The biomarkers aim to help interpret the outcomes, and further explain clinical differences in the above-measured outcomes
Ascorbate trough levels	Plasma ascorbate at baseline (0 hours) levels at 24 hours, 48 hours, 96 hours and 168 hours	The PK of ascorbate is still unknown in the target patient population
Alive and free of significant respiratory failure through 28-days	At 28-days is the patient alive and not in respiratory failure, the principal cause of death by COVID-19	Respiratory failure defined as at least one of the following: 
 • Endotracheal intubation and mechanical ventilation • •Oxygen delivered by high-flow nasal

		
cannula (heated, humidified)
 
 • Oxygen delivered via reinforced nasal cannula at flow rates >20L/min with fraction of delivered oxygen ≥ 0.5) • Noninvasive positive pressure ventilation (CPAP or BIPAP) • Extracorporeal membrane oxygenation (ECMO of any type)

Alive and free of mechanical ventilation at 28-days
	
Proportion of patients alive and free of invasive mechanical ventilation at 28-days.
	
Is the patient dependent on mechanical ventilation by 28-days, that is development of significant chronic respiratory failure

WHO COVID-19, 9-point Ordinal Outcome Scale		
Patient State	Descriptor	Score
Uninfected	No clinical or virologic evidence of infection	0
Ambulatory	No limitation of activities	1
	Limitation of Activities	2
Hospitalized mild disease	Hospitalized, no oxygen therapy	3

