8.1.1 Venous Blood Collection Timeline

Septic patients exhibit subnormal plasma ascorbate levels. Phase I studies performed at Virginia Commonwealth University (VCU) show mean ascorbate levels of 17.5 μ M (normal human ascorbate levels 60 to 70 μ M), while some other centers report undetectable plasma vitamin C in COVID-19 patients. **Baseline ascorbate levels will be drawn, before the initiation of any infusion with subsequent trough levels for PK monitoring.**

The target plasma range for modifying pro-inflammatory biomarkers and for attenuating vascular injury was obtained from the phase I safety trial and is greater than 500 μ M as measured 24 hours after initiation of Vitamin C infusion. The day 2 – 7 plasma ascorbate levels are expected to be between 500 to 1000 μ M based on prior pharmacokinetic studies generated during the phase I trial (VCU trial was entitled: Vitamin C Infusion in Human Sepsis).

Blood drawn for ascorbate levels and biomarkers will occur at hour 0 (prior to the first infusion), **hour 48 (+ or – 3 hours as long as it is drawn prior to Infusion 9), hour 96 (+ or – 3 hours as long as it is drawn at least 3 hours post Infusion 16), and hour 168 (+ or – 6 hours).**

Schedule

	Baseline (hour 0)	Treatment days 1-4 (hour 24)	Treatment days 4-7	Days 7-14	Days 14-21	Phase 1 Study end (day 28)	Phase 2 Day 60 and Day 90
Death from ANY cause	X	X	X	X	X	X	X
Alive and Free of any	X	X	X	X	X	X	

respiratory failure							
Alive and free from invasive mechanical ventilation	X	X	X	X	X	X	
AKI (y/n) and stage	X	X	X	X	X	X	
WHO COVID-19 SCALE	X	X	X	X	X	X	X
Concomitant medication use(a)	X	X	X	X	X	X	
Plasma levels (b)	X	X	X	X	X	X	
Vital signs (c)	X	X	X	X	X	X	
Clinical assessment for kidney stone symptoms	X	X	X	X	X	X	
qSOFA score	X	X	X	X	X	X	
Ins/Outs	X	X	X	X	X	X	
Ventilator status / oxygen (e)	X	X	X	X	X	X	
Ventilator-free days	X	X	X	X	X	X	
AKI-free days	X	X	X	X	X	X	
24-hour urine collection			X5, X7	X14*	X21*	X28*	
Ventilator and drip data	X	X	X	X	X	X	
AE/tolerance (g)		X	X				
Mortality (h)	X	X	X	X	X	Date/time	
Discharge (i)	X	X	X	X	X	Date/time	
WHO COVID-19 Scale	X	X	X	X	X	X	

Footnotes:

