8.2 Safety and Other Assessments

The following data will provide the basis for assessing protocol compliance and safety as well as between-group differences in several efficacy variables. Data for each of the variables will be recorded on the days shown in the time-events schedule table. This trial will use the Common Terminology Criteria for Adverse Events version 5 (CTCAE v. 5) to assess safety and severity of symptoms.

8.2.1 Every 24 hours for as long as the patient is in the hospital: input/output, hypoglycemic events, creatinine, worst vital signs, and oxygen requirement, dialysis, admission to the ICU or need for mechanical ventilation. COVID-19 WHO ordinal status, daily serum chemistries, CBC, magnesium, telemetry ECG tracing monitoring and continuous oximetry monitoring. Patients are monitored for gastrointestinal tolerability (i.e., nausea, diarrhea) and for other adverse events (i.e., rash, headache) and agent will be **stopped** for CTCAE V5 for grade 3 or higher, while the study monitoring will continue.

8.2.2 Every, 24, 48, hours: Acute Kidney Injury-free days, Worst vital signs, Serum electrolytes, chemistries, concurrent medications AE/SAE Assessments, Weight, Bilirubin, Oxygenation Data, Kidney stone symptoms

8.2.3 Every 7, 14, 21 and 28 days: Required: Ventilator Free Days to Day 28, All-Cause Mortality to Day 28, oxygenation indices, oxygen device, use of dialysis. COVID-19 WHO ordinal status.

8.2.4 Sixty and 90 Days: All-cause mortality, routine evaluations of organ function, functional status

8.2.5 All patients will be treated **at minimum** subcutaneous unfractionated heparin for thrombo-prophylaxis (5000 units TID). Anticoagulation may be escalated by the treating physicians based on clinical and laboratory variables, such as the D-Dimer and the thromboelastogram (TEG). If suspicion of clotting arises immediate thromboelastography (TEG) will be performed to determine if clotting is ongoing. If TEG supports clotting suspicions doppler ultrasound **of the appropriate venous site** will be performed.

8.2.6 Assessment of hepatic safety: Hepatic transaminases will be monitored at baseline, day 2 and day 3 or the study. Persistent elevations will lead to: 1) discussion with ward staff, 2) will lead to right upper quadrant ultrasonography, and 3) Consultation from the Hepatology service.

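### The primary WHO score is scheduled inconsistently at days 60 and 90, is limited to inpatients in one schedule at day 28, and has no stated scoring convention after discharge

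*Combined protocol and SAP*

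**What the plan says.** **Endpoint.** The synopsis compares mean WHO scores "between the two populations at 28, 60 and 90 days". Section 3.1 lists "MEAN SCORE ON DAY 28, 60 AND 90".

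**Days 60 and 90.**
- In the SoA, the row "WHO-COVID-19 SCALE" has no entry under Day 60&90.
- The section 8.1.1 schedule has two WHO rows. The upper one, "WHO COVID-19 SCALE", is marked in the day 60/90 column; the one at the foot of the table is not.
- Section 8.2.4 lists mortality, organ function and functional status. The Phase 2 list under 8.1.1 asks only about vital status and details of death.
- Participant Duration and the End of Study Definition in the synopsis name a day-90 contact only. Sections 4.1 (item 5) and 4.4 name days 60 and 90.

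**Day 28.**
- The SoA marks the score R* from day 8 to day 28, defined as "R* IF the patient is in the hospital".
- Section 8.2.1 lists the WHO status "Every 24 hours for as long as the patient is in the hospital". Section 8.2.3 lists it again at days 7, 14, 21 and 28, under the word Required and with no in-hospital condition. Both 8.1.1 rows are marked at day 28 without a condition.

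**Scoring.** Table 1 gives one line each for scores 0, 1 and 2; score 0 is "No clinical or virologic evidence of infection". Section 9 (Missing Data) says that the scale takes in death and discharge, but assigns no value to a discharged patient.

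**The concern.** Staff work from the schedules. If these disagree about whether and for whom the primary outcome is recorded, its completeness depends on which table is open. At days 60 and 90 the main schedule does not ask for the score at all, and a functional score not obtained at the time may not be recoverable afterwards.

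For discharged survivors there is a second problem. Scores 0, 1 and 2 enter a comparison of means as numbers, so the convention chosen affects the size of the estimate. If it is not fixed in advance, part of the primary result of a trial whose stated purpose is safety rests on an undocumented choice.

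**Working it through.** **1. Are the blanks real?** The SoA has nine assessment columns. Its WHO row has eight entries: five R, three R*, and nothing under Day 60&90. Other rows do carry marks in that column (EKG, chest imaging, tracheostomy, death, DNR, phone follow-up), so a lost column is an unlikely explanation. In 8.1.1 the upper WHO row has seven marks for seven columns, and the lower has six.

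**2. What each source yields**

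| Source | Day 28 | Days 60/90 |
|---|---|---|
| Synopsis and 3.1 (endpoint) | required | required |
| SoA | inpatients only | blank |
| 8.1.1, upper row | marked | marked |
| 8.1.1, lower row | marked | blank |
| 8.2.3 / 8.2.4 | listed (8.2.3) | omitted (8.2.4) |
| Phase 2 list | not applicable | omitted |

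At days 60/90 a single schedule row supports collection, and its duplicate contradicts it. Deaths (score 8) are captured in the SoA through day 90, so the gap concerns survivors.

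**3. What is known at day 28.** The synopsis and section 4.4 follow all subjects to day 28 by chart review. The SoA also has an unconditional day 22-28 row for hospitalization status and discharge date. Each patient can therefore be placed as dead, in hospital or discharged. The missing piece is the choice among 0, 1 and 2.

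**4. Can 0, 1 and 2 be assigned?** A patient without evidence of infection may or may not have limited activity, so 0 overlaps with 1 and 2. Neither schedule lists a SARS-CoV-2 test to support 0. Functional status (8.2.4) and the PROMIS phone measure (SoA) appear only at days 60/90, and neither is mapped to the scale.

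**5. The yardstick.** Section 9 states 96% power for a 1-point difference with 30 per arm and two-sided alpha 0.04. The readable text gives no SD (it may be in a figure not shown). An SD of 1.0 gives 96.0% on the noncentral t. The figure is therefore consistent with that SD but not independently reproduced. Only the 1-point target is used below.

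**6. Size of the scoring choice.** The documents give no discharge rates, so these are assumed. If all discharged survivors receive one score c, they contribute c × f to an arm mean, where f is the discharged share. Changing c shifts the between-arm contrast by (change in c) × (difference in f):
- 0 rather than 2: 2 × 0, 2 × 0.10, 2 × 0.20 = 0, 0.2, 0.4 points.
- 1 rather than 2: 1 × 0, 1 × 0.10, 1 × 0.20 = 0, 0.1, 0.2 points.

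**7. Conditional illustration: discharged survivors dropped at day 28.** This applies only if the SoA is followed literally and section 9 is ignored. Assume death 8, in-hospital mean 4.9, discharged mean 1.5, with d the share dead and h the share in hospital. All-patient mean = 8d + 4.9h + 1.5(1 − d − h). Recorded-only mean = (8d + 4.9h)/(d + h).
- d 40% v 20%, h 20% v 20%: 4.78 − 3.48 = 1.30 becomes 6.97 − 6.45 = 0.52.
- d 30% v 30%, h 30% v 10%: 4.47 − 3.79 = 0.68 becomes 6.45 − 7.225 = −0.78.
- d 40% v 20%, h 10% v 30%: 4.44 − 3.82 = 0.62 becomes 7.38 − 6.14 = 1.24.

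With in-hospital means of 4 to 6 and discharged means of 1 to 2, the three recorded-only contrasts run 0.33 to 0.67, −1.0 to −0.5, and 0.8 to 1.6. The distortion can go either way.

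**The case against.** A reader might infer that discharged patients drop out of the day-28 primary analysis, leaving a comparison of inpatients and deaths that is selected by outcome. The documents do not support that as the plan's intention. Section 8.2.3 requires the score at day 28, both 8.1.1 rows mark it, and section 9 implies that discharged patients are scored. Step 7 is therefore a risk of following one table literally, not a description of the planned analysis.

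A reader might also take the plain R on rows such as "Alive and Free of ANY Respiratory Failure (yes/no)" as proof that the in-hospital limit on the WHO row was deliberate. That inference is weak: CBC, vital signs and vasopressor rates also carry unconditional marks through day 28, and these cannot be meant for discharged patients. In addition, the day 5-28 column headers carry a double asterisk with no legend in the readable text, so the day-28 restriction may be qualified somewhere not visible. The Day 60&90 header carries no such mark.

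Nor is it right that nothing separates 0, 1 and 2. Table 1 distinguishes 1 from 2 by limitation of activities, and functional status at days 60/90 could inform that. The scoring effect is also smaller than it may look: at 50% discharged, moving from 2 to 0 shifts an arm mean by 1.0 point, but the contrast does not move if discharge is equal in the arms.

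What stands is the conflict at days 60/90, the mismatch between the SoA and 8.2.3 at day 28, and the lack of a scoring convention and data source after discharge. Section 9 supplies no value, and it also says that clinical data missing because of discharge will not be imputed, so there is no clear fallback.

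**Conclusion.** The point holds, with days 60 and 90 as its main limb. Two of the three primary time points have no consistent instruction to score survivors, and the main schedule has none. At day 28 the defect is narrower: one table restricts the score to inpatients against the others, and a discharged survivor's value within 0 to 2 is left open.

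Under the assumed discharge differences of 0 to 20 percentage points, and with every discharged survivor given the same score, the convention is worth 0 to 0.4 points against a 1-point target. The larger distortions from dropping discharged survivors depend on assumed rates and on a reading that section 9 disfavours, so they should not be taken as the expected effect. The point is still a must-fix, because it concerns whether the primary outcome is recorded at all and the remedy is cheap.

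A related minor point is the analysis trigger. Phase 1 ends at day 28, but section 9 ties its analysis to the 60th patient finishing enrollment and being discharged. A reader might infer that the analysis would precede that patient's day 28. The wording is ambiguous, since the same sentence refers to phase 1, and it needs only clarification.

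**What to change.** - **(a) Days 60/90.** Mark the WHO score in the SoA Day 60&90 column, add it to 8.2.4 and the Phase 2 list, and collect it at the contacts already planned. Align Participant Duration and the synopsis End of Study Definition with the day-60 contact in 4.1 and 4.4.
- **(b) Day 28.** Remove the in-hospital condition for the day-28 score so that every participant is scored, and delete the conflicting duplicate WHO row in 8.1.1.
- **(c) Scoring.** State one convention for 0, 1 and 2 after discharge and its data source, either existing records or a brief call. Say whether 0 may be used when no SARS-CoV-2 test has been done.
- **(d) Clarification.** State that the phase 1 analysis starts only once the 60th patient has reached day 28.

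Cost: a protocol amendment, one item added to planned contacts, at most a short wait before the phase 1 analysis and, only if calls are chosen in (c), one short day-28 call per discharged survivor.
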